8.0 Dosage Modification Based on Adverse Events

Strictly follow the modifications in this table for the first **two** cycles, until individual treatment tolerance can be ascertained. Thereafter, these modifications should be regarded as guidelines to produce mild-to-moderate, but not debilitating, side effects. If multiple adverse events are seen, administer dose based on greatest reduction required for any single adverse event observed. Reductions or increases apply to treatment given in the preceding cycle and are based on adverse events observed since the prior dose.

ALERT: *ADR reporting may be required for some adverse events (See Section 10)*

8.1 Dose Modifications for Rucaparib (Based on Adverse Events in Tables 8.2 and 8.3)

Starting Dose Level	1 st Dose Modification	2 nd Dose Modification
600 mg BID	500 mg BID	400 mg BID
400 mg BID	300 mg BID	200 mg BID
300 mg BID	200 mg BID	300 mg QD
200 mg BID	300 mg QD	200 mg QD

NOTE: No more than two dose reductions are allowed.

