Grade ≥ 4	
 • Hold rucaparib • Monitor liver function tests weekly until resolution to \leq Grade 2 		Resume with a dose reduction and monitor liver function tests weekly for 3 weeks after restarting.

a. NCI-CTCAE = National Cancer Institute - Common Terminology Criteria for Adverse Events, version 4.03

b. Treatment with rucaparib should be held until the toxicity resolves to \leq CTCAE Grade 2. Twice daily dosing may then be resumed at either the same dose or a lower dose, per investigator discretion. If treatment is resumed at the same dose, and the patient experiences the same toxicity, the dose should be reduced following resolution of the event to \leq CTCAE Grade 2. If the patient continues to experience toxicity, additional dose reduction steps are permitted; however, the investigator should contact ACCRU (see Protocol Resource page) before reducing to 300 mg BID. If a patient continues to experience toxicity despite dose reduction steps to 300 mg BID, or if dosing with rucaparib is interrupted for $>$ 14 consecutive days due to toxicity, treatment should be discontinued, unless otherwise agreed between the investigator and ACCRU.

8.3 Dose Modifications for Non-Hematologic Toxicities Other than grade 3 ALT/AST (follow recommendation by Table 8.22), Fatigue and Grade 3 Anorexia^{a, d}

Worst Toxicity by CTCAE Grade*	na1-IRI	5-FU
Grade 1 diarrhea ^b	Continue same dose	Continue same dose
Grade 1 or 2 including diarrhea (except alopecia, nausea and vomiting)	Withhold na1-IRI then resume once resolved to grade 1 at 100% of previous dose	Withhold 5-FU, then resume once resolved to grade 1 at 100% of previous dose, except for Grade 2 hand foot syndrome, Grade 2 cardiac toxicity, or any grade neurocerebellar toxicity
Grade 3 or 4, including diarrhea ^c (except alopecia, nausea and vomiting)	Withhold na1-IRI then resume once resolved to grade 1 per below: 1 st occurrence: Reduce dose to by 25% 2 nd occurrence: Reduce dose another 25% (50% of original dose)	Withhold 5-FU then resume once resolved to grade 1 per below: 1 st occurrence: Reduce dose by 25% 2 nd occurrence: Reduce dose another 25% (50% of original dose) *except for Grade 3 or 4 hand foot syndrome

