Grade 3 or 4 nausea and/or vomiting, despite anti-emetic therapy	Optimize anti-emetic therapy AND reduce dose to 50 mg/m ² , if starting dose is 70 mg/m ² .. If the patient is already receiving 50 mg/m ² , reduce dose to 43 mg/m ² , ^c	Optimize anti-emetic therapy AND reduce dose by 25%; if the patient is already receiving a reduced dose, reduce dose an additional 25% ^e
Grade 2 hand foot syndrome	100% of previous dose	1 st occurrence: Reduce dose by 25% 2 nd occurrence: Reduce dose another 25% (50% of original dose) ^d
Grade 3 or 4 hand foot syndrome	1 st occurrence: Reduce dose to 50 mg/m ² , if starting dose is 70 mg/m ² . 2 nd occurrence: Reduce dose to 43 mg/m ²	Discontinue therapy
Any grade neurocerebellar or ≥ Grade 2 cardiac toxicity	No dose modifications required ^d	Discontinue therapy
Sensory neuropathy	No dose modifications required ^d	No dose modifications required ^d

* Located at [REDACTED]

^a Fatigue and Grade 3 anorexia do not require dose modification.

^b Grade 1 diarrhea: 2-3 stools/day > pretreatment.

^c Grade 2 diarrhea: 4-6 stools/day > pretreatment; Grade 3 diarrhea: 7-9 stools/day > pretreatment; Grade 4 diarrhea: > 10 stools/day > pretreatment.

^d Any toxicity ≥ Grade 2, except anemia and alopecia, can justify a dose reduction if medically indicated.

^e Patients who require more than 2 dose reductions must be withdrawn from the study.

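### Table 8.3 gives two incompatible 5-FU instructions, stop and resume at a reduced dose, for a grade 3–4 cardiac or neurocerebellar event

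*Combined protocol and SAP*

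**What the plan says.** Rows in Table 8.3 (Section 8.3, non-hematologic toxicities) are chosen by "Worst Toxicity by CTCAE Grade". Three 5-FU cells matter.

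- **Grade 1–2 row.** Withhold, then resume at full dose after recovery to grade 1, "except for Grade 2 hand foot syndrome, Grade 2 cardiac toxicity, or any grade neurocerebellar toxicity".
- **Grade 3–4 row.** "Withhold 5-FU then resume once resolved to grade 1 per below", at a 25% reduction for a first occurrence and a further 25% for a second. The row label leaves out alopecia, nausea and vomiting. The 5-FU cell adds one exception: "except for Grade 3 or 4 hand foot syndrome".
- **Event-specific row.** For "Any grade neurocerebellar or ≥ Grade 2 cardiac toxicity" the instruction is "Discontinue therapy".

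Section 8.0 sets the force of the table. It opens "Strictly follow the modifications in this table for the first" two cycles, and then says "Thereafter, these modifications should be regarded as guidelines". Its tie-break, to apply the greatest reduction, is worded for a patient with several adverse events.

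**The concern.** The event-specific row covers cardiac toxicity from grade 2 upward and neurocerebellar toxicity at every grade, so it includes grades 3 and 4. The general grade 3–4 row also includes them, because neither its label nor its 5-FU cell takes them out. One event then carries both a stop instruction and a resume instruction.

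The grade 1–2 row does take these toxicities out, so the matching exception appears to have been left off the row below. Read literally, the result is inverted by severity: a grade 2 cardiac event has only the stop instruction, while a grade 3–4 event also has a route back to 5-FU. What is at stake is re-exposing a patient to 5-FU after a serious cardiac event during the cycles in which sites are told to follow the table strictly.

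**Working it through.** The plan states no figure to reproduce. The check is a reading of the rows against each other, followed by simple dose arithmetic.

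**Step 1: which 5-FU instructions apply, by event and grade (Table 8.3)**

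| Event | General row | Specific row | Consistent? |
|---|---|---|---|
| Cardiac, grade 2 | excepted | stop | yes |
| Neurocerebellar, grade 1–2 | excepted | stop | yes |
| Hand foot syndrome, grade 3–4 | excepted | stop | yes |
| Cardiac, grade 3–4 | resume at reduced dose after recovery to grade 1 | stop | **no** |
| Neurocerebellar, grade 3–4 | resume at reduced dose after recovery to grade 1 | stop | **no** |

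The overlap is clearest for cardiac events. For neurocerebellar events the point at which the general row allows 5-FU to resume, grade 1, still lies within the specific row, so the stop instruction continues to apply on its face.

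**Step 2: is there a precedence rule?** None is stated. The tie-break in Section 8.0 addresses several events in one patient, not one event that meets two rows. Nor does the table rely on an unstated rule that the specific row wins: hand foot syndrome has its own rows and is still excepted in both general 5-FU cells.

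**Step 3: difference in dose.** Sections 7.12 and 7.13 set 5-FU at 2400 mg/m² for Phase Ib and Phase II.

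- Before recovery to grade 1: 0 mg/m² under both rows, so no difference.
- After recovery, first occurrence: 0.75 × 2400 = 1800 mg/m² (general row) against 0 (specific row).
- After recovery, second occurrence: 0.50 × 2400 = 1200 mg/m² against 0.

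**Step 4: infusions affected in the binding window.** Section 7.1 gives 5-FU on days 1 and 15 of a 28-day cycle. Over cycles 1 and 2 these are study days 1, 15, 28 + 1 = 29 and 28 + 15 = 43, so 14 days apart. For an event starting at the day 1 infusion, with later infusions on their scheduled days:

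| Recovery to grade 1 | Infusions at which the rows differ |
|---|---|
| within 14 days | 3 (days 15, 29, 43) |
| 15–28 days | 2 (days 29, 43) |
| 29–42 days | 1 (day 43) |
| more than 42 days | 0 |

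**Step 5: frequency.** Section 15.37 lists cardiac and cerebellar items for 5-FU among toxicities below 1%, without grade, and links the cerebellar ones mainly to intracarotid infusion. The documents do not support a probability for this trial, and none is claimed.

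**The case against.** The strongest reply is that the table already shows what to do. The specific row names the event, takes effect at onset and is final, so a site that follows it never reaches the resume step. To restart 5-FU, an investigator would have to pass over the row that names the patient's event and accept that grade 4 cardiac toxicity is handled more leniently than grade 2. The greatest-reduction principle in Section 8.0 points the same way even though its wording does not cover this case. Section 3.24 already excludes several uncontrolled cardiac conditions, and after cycle 2 the table is only guidance. The infusion counts rest on an event at the very first dose, and the neurocerebellar half of the overlap is weak. The nal-IRI column has a similar overlap, where the intended action is less obvious, and the proposed change leaves it alone.

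Most of this stands, and it keeps the weight small. It does not remove the contradiction. A cell that lists exceptions and names only one can be read as complete, and in the first two cycles sites are told to follow the table strictly. That the intended reading is clear is a reason to write it down. The nal-IRI overlap is a separate clinical question and does not make the 5-FU correction unsound.

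**Conclusion.** The concern holds. As written, Table 8.3 contradicts itself on 5-FU for grade 3–4 cardiac toxicity and, less sharply, for grade 3–4 neurocerebellar toxicity. Discontinuation is evidently intended, so this is a drafting omission with a small but real patient-safety side.

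The size is that of Steps 3 and 4: no difference until recovery, then a reduced dose instead of none at no more than three infusions in the binding window. That count assumes onset at the first infusion, an unchanged infusion calendar and a site that follows the general row. The design, the error rates and the primary analysis are unaffected. The correction should be made because the safe direction is clear and the cost is close to nil.

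**What to change.** In the 5-FU cell of the grade 3–4 row of Table 8.3, extend the exception "except for Grade 3 or 4 hand foot syndrome" so that it also names grade 3–4 cardiac toxicity and grade 3–4 neurocerebellar toxicity, with a pointer to the rows below that require 5-FU to be discontinued. This brings the cell into line with the grade 1–2 row above it.

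A blanket sentence saying that specific rows override general ones is not advised. It would loosen the nal-IRI and sensory neuropathy rules, where the specific rows call for no dose change; those cells are for the sponsor's clinicians to settle.

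The cost is one phrase in one table cell, with no added patients, visits or procedures.

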9.0 Ancillary Treatment/Supportive Care

- 9.1 Antiemetics may be used at the discretion of the attending physician. NOTE: 5-HT3 antagonists is specifically recommended as an antiemetic for rucaparib, however, patients can be treated per the treating site's institutional guidelines.
- 9.2 Blood products and growth factors should be utilized as clinically warranted and following institutional policies and recommendations. The use of growth factors should follow published guidelines of the American Society of Clinical Oncology (ASCO), Recommendations for the Use of WBC Growth Factors: American Society of Clinical Oncology Clinical Practice Guideline Update. J Clin Oncol 2015;33:3199-3212.
- 9.3 Patients should receive full supportive care while on this study. This includes blood product support, antibiotic treatment, and treatment of other newly diagnosed or concurrent medical conditions. All blood products and concomitant medications such as antidiarrheals, analgesics, and/or antiemetics received from the first day of study treatment administration until 30 days after the final dose will be recorded in the medical records.
- 9.4 Diarrhea: This could be managed conservatively with loperamide. The recommended dose of loperamide is 4 mg at first onset, followed by 2 mg every 2-4 hours until diarrhea free (maximum 16 mg/day). Treating physicians can consider administering intravenous or subcutaneous atropine 0.25-1 mg (unless clinically contraindicated) for early onset diarrhea or any severity.

In the event of grade 3 or 4 diarrhea, the following supportive measures are allowed: hydration, octreotide, and antidiarrheals.

If diarrhea is severe (requiring intravenous rehydration) and/or associated with fever or severe neutropenia (grade 3 or 4), broad-spectrum antibiotics must be prescribed. Patients with severe diarrhea or any diarrhea associated with severe nausea or vomiting **should be hospitalized** for intravenous hydration and correction of electrolyte imbalances.

10.0 Adverse Event (AE) Reporting and Monitoring

Definitions

Adverse Event

Any untoward medical occurrence associated with the use of a drug in humans, whether or not considered drug related.

Suspected Adverse Reaction

Any adverse event for which there is a reasonable possibility that the drug caused the adverse event.

Expedited Reporting

Events reported to sponsor within 24 hours, 5 days or 10 days of study team becoming aware of the event.

Routine Reporting

Events reported to sponsor via case report forms

Events of Interest

Events that would not typically be considered to meet the criteria for expedited reporting, but that for a specific protocol are being reported via expedited means in order to facilitate the review of safety data (may be requested by the FDA or the sponsor).

10.1 Adverse Event Characteristics

CTCAE term (AE description) and grade: The descriptions and grading scales found in the revised NCI Common Terminology Criteria for Adverse Events (CTCAE) version 4.0 will be utilized for AE reporting. All appropriate treatment areas should have access to a copy of the CTCAE version 4.0. A copy of the CTCAE version 4.0 can be downloaded from the CTEP web site:

- a. Adverse event monitoring and reporting is a routine part of every clinical trial.
- b. Identify the grade and severity of the event using the CTCAE version 4.0
- c. Determine whether the event is expected or unexpected (see Section 10.2).
- d. Determine if the adverse event is related to the study intervention (agent, treatment or procedure) (see Section 10.3).
- e. Determine whether the event must be reported as an expedited report. If yes, determine the timeframe/mechanism (see Section 10.4).
- f. Determine if other reporting is required (see Section 10.5).
- g. Note: All AEs reported via expedited mechanisms must also be reported via the routine data reporting mechanisms defined by the protocol (see Sections 10.6 and 18.0).

Each CTCAE term in the current version is a unique representation of a specific event used for medical documentation and scientific analysis and is a single MedDRA Lowest Level Term (LLT).

NOTE: A severe AE, as defined by the above grading scale, is NOT the same as serious AE which is defined in the table in Section 10.4.

10.2 Expected vs. Unexpected Events

Expected events - are those described within the Section 15.0 of the protocol, the study specific consent form, package insert (if applicable), and/or the investigator brochure, (if an investigator brochure is not required, otherwise described in the general investigational plan).

Unexpected adverse events or suspected adverse events are those not listed in Section 15.0 of the protocol, the study specific consent form, package insert (if applicable), or in the investigator brochure (or are not listed at the specificity or severity that has been observed); if an investigator brochure is not required or available, is not consistent with

the risk information described in the general investigational plan.

Unexpected also refers to adverse events or suspected adverse reactions that are mentioned in the investigator brochure as occurring with a class of drugs but have not been observed with the drug under investigation.

10.3 Assessment of Attribution

When assessing whether an adverse event is related to a medical treatment or procedure, the following attribution categories are utilized:

Definite - The adverse event *is clearly related* to the agent(s)/treatment.
Probable - The adverse event *is likely related* to the agent(s)/treatment.
Possible - The adverse event *may be related* to the agent(s)/treatment.
Unlikely - The adverse event *is doubtfully related* to the agent(s)/treatment.
Unrelated - The adverse event *is clearly NOT related* to the agent(s) treatment.

Events determined to be possibly, probably or definitely attributed to a medical treatment suggest there is evidence to indicate a causal relationship between the drug/device and the adverse event.

10.31 Special Situations for Expedited Reporting

10.311 EXPECTED Serious Adverse Events: Protocol Specific Exceptions to Expedited Reporting

For Phases I and Ib of this study, all Serious Adverse Events will be subject to Expedited Reporting (as defined in Section 10.41). The list of Expected Serious Adverse Events and associated grades will be reviewed and determined by the study team after the completion of the Phase 1b portion of the study.

10.312 Death

- Any death occurring within 30 days of the last dose, regardless of attribution to an agent/intervention under an IND/IDE requires expedited reporting within 24-hours.
- Any death occurring greater than 30 days with an attribution of possible, probable, or definite to an agent/intervention under an IND/IDE requires expedited reporting within 24-hours.
- **Reportable categories of Death**
 - Death attributable to a CTCAE term.

- Death Neonatal: A disorder characterized by cessation of life during the first 28 days of life.
- Death NOS: A cessation of life that cannot be attributed to a CTCAE term associated with Grade 5.
- Sudden death NOS: A sudden (defined as instant or within one hour of the onset of symptoms) or an unobserved cessation of life that cannot be attributed to a CTCAE term associated with Grade 5.
- Death due to progressive disease should be reported as **Grade 5 “Neoplasms benign, malignant and unspecified (including cysts and polyps) – Other (Progressive Disease)”** under the system organ class (SOC) of the same name. Evidence that the death was a manifestation of underlying disease (e.g., radiological changes suggesting tumor growth or progression: clinical deterioration associated with a disease process) should be submitted.

10.313 Secondary Malignancy

- A **secondary malignancy** is a cancer caused by treatment for a previous malignancy (e.g., treatment with investigational agent/intervention, radiation or chemotherapy). A secondary malignancy is not considered a metastasis of the initial neoplasm.
- All secondary malignancies that occur following treatment with an agent under an IND/IDE to be reported. Three options are available to describe the event:
 - Leukemia secondary to oncology chemotherapy (e.g., acute myeloid leukemia [AML])
 - Myelodysplastic syndrome (MDS)
 - Treatment related secondary malignancy
- Any malignancy possibly related to cancer treatment (including AML/MDS) should also be reported via the routine reporting mechanisms outlined in each protocol.

10.314 Second Malignancy

- A second malignancy is one unrelated to the treatment of a prior malignancy (and is NOT a metastasis from the initial malignancy). Second malignancies require ONLY routine reporting.

10.315 Pregnancy

If a patient becomes pregnant during the study the investigator is to stop dosing with study drug(s) immediately.

A pregnancy is not considered to be an AE or SAE; however, any pregnancy occurring in a study patient or partner of a study patient during study participation or within 6 months of last dosing must be reported within the same timelines as an SAE.

A pregnancy should be followed through to outcome, whenever possible.

Prior to obtaining private information about a pregnant woman and her infant, the investigator must obtain consent from the pregnant woman and the newborn infant's parent or legal guardian before any data collection can occur. A consent form will need to be submitted to the IRB for these subjects if a pregnancy occurs. If informed consent is not obtained, no information may be collected.

In cases of fetal death, miscarriage or abortion the mother is the patient. In cases where the child/fetus experiences a serious adverse event other than fetal death, the child/fetus is the patient.

NOTE: When submitting the MedWatch 3500A Form for "pregnancy," "pregnancy loss," or "neonatal loss," the potential risk of exposure of the fetus to the investigational agent(s) or chemotherapy agent(s) should be documented in the "Description of Event" section. Include any available medical documentation.

10.4 Expedited Reporting Requirements for Studies using Commercial Agent(s) ONLY:

Expedited Reporting Requirements for Adverse Events that Occur in a Non-IND/IDE trial within 30 Days of the Last Administration of a Commercial Agent^{1,2}

FDA REPORTING REQUIREMENTS FOR SERIOUS ADVERSE EVENTS (21 CFR Part 312)

NOTE: Investigators **MUST** immediately report to the sponsor **ANY** Serious Adverse Events, whether or not they are considered related to the investigational agent(s)/intervention (21 CFR 312.64)

An adverse event is considered serious if it results in **ANY** of the following outcomes:

- 1) Death
- 2) A life-threatening adverse event
- 3) An adverse event that results in inpatient hospitalization or prolongation of existing hospitalization for ≥ 24 hours
- 4) A persistent or significant incapacity or substantial disruption of the ability to conduct normal life functions
- 5) A congenital anomaly/birth defect.
- 6) Important Medical Events (IME) that may not result in death, be life threatening, or require hospitalization may be considered serious when, based upon medical judgment, they may jeopardize the patient or subject and may require medical or surgical intervention to prevent one of the outcomes listed in this definition. (FDA, 21 CFR 312.32; ICH E2A and ICH E6).

ALL SERIOUS adverse events that meet the above criteria **MUST** be immediately reported to the sponsor within the timeframes detailed in the table below.

Hospitalization	Grade 1 Timeframes	Grade 2 Timeframes	Grade 3 Timeframes	Grade 4 & 5 Timeframes
Resulting in Hospitalization ≥ 24 hrs		7 Calendar Days		24-Hour 3 Calendar Days
Not resulting in Hospitalization ≥ 24 hrs	Not required		7 Calendar Days	

Expedited AE reporting timelines are defined as:

- “24-Hour; 3 Calendar Days” - The AE must initially be reported via MedWatch within 24 hours of learning of the AE, followed by a complete expedited report within 3 calendar days of the initial 24-hour report.
- “7 Calendar Days” - A complete expedited report on the AE must be submitted within 7 calendar days of learning of the AE.

¹Serious adverse events that occur more than 30 days after the last administration of investigational agent/intervention and have an attribution of possible, probable, or definite require reporting as follows:

Expedited 24-hour notification followed by complete report within 3 calendar days for:

- All Grade 4, and Grade 5 AEs

Expedited 7 calendar day reports for:

- Grade 2 adverse events resulting in hospitalization or prolongation of hospitalization
- Grade 3 adverse events

² For studies using PET or SPECT IND agents, the AE reporting period is limited to 10 radioactive half-lives, rounded UP to the nearest whole day, after the agent/intervention was last administered. Footnote “1” above applies after this reporting period.

Effective Date: May 5, 2011

Special Instructions:

• An increased incidence of an expected adverse event (AE) is based on the patients treated for this study at their site. A list of known/expected AE's are reported in the package insert or the literature, including AE's resulting from a drug overdose.

• Follow site-specific reporting guidelines.

- Submit MedWatch form 3500A

[REDACTED] or found on the ACCRU web site) along with the MedWatch Fax Cover Sheet (found on the ACCRU web site) to ACCRU Safety via email at: [REDACTED] ACCRU Safety will forward to Ipsen and Clovis, as follows:

Clovis: email [REDACTED] or FAX: [REDACTED]
NOTE: SAE's must be sent to Clovis within 24 hours of receipt by ACCRU. Pregnancies must be reported within 48 hours of receipt by ACCRU.

Ipsen: email [REDACTED]

• ACCRU Safety will forward to ACCRU IND Coordinator [REDACTED] as appropriate. The ACCRU IND Coordinator will assist the sponsor-investigator in notifying the FDA if required.

• Clovis AEs of Special Interest (AESI) for Rucaparib

AESI (serious or non-serious) are defined as AEs of scientific and medical concern specific to rucaparib, for which ongoing monitoring and rapid communication by the Sponsor-investigator to Clovis can be appropriate. Such an event might warrant further investigation in order to characterize and understand it. Depending on the nature of the event, rapid communication by the Sponsor-Investigator to other parties (e.g., regulators) might also be warranted. AESI's should be reported within 24 hours of awareness to the ACCRU SAE Coordinator using the MedWatch form 3500A. Within 24 hours, the ACCRU SAE Coordinator will report to Clovis

Clovis AEs of Special Interest for this trial include:

1. Leukemia secondary to oncology chemotherapy (e.g. Acute Myeloid Leukemia [AML])
2. Myelodysplastic syndrome (MDS)
3. Pneumonitis

